# BIOLOGIC USAGE PATTERNS, CLINICAL OUTCOMES AND HEALTHCARE UTILIZATION (CLEAR)

The clinical and health resources effects of continuing, switching, and stopping an initiation biologic

[figure not shown]
Date: 03/08/2021

[name]

[figure not shown]
[contact] Website http://optimumpatientcare.org/

Title	Biologic Usage Patterns, Clinical Outcomes and Healthcare Resource Utilization	
Subtitle	The clinical and health resources effects of continuing, switching, and stopping an initiation biologic (CLEAR)	
Protocol version number	V0.7	
Medicinal product	Not applicable	
Product code	Not applicable	
Marketing authorization holder/numbers	Not applicable	
Study aims and objectives	Aim: To investigate the effects of distinct patterns of biologic use in a real-life cohort of patients with severe asthma.  Objectives:  1. To describe the demographic and clinical characteristics, including the extent of T2 phenotype, in five groups of patients with severe asthma, including those who do not initiate a biologic when eligible, and do not initiate and are not eligible, and between those who initiate: those who stop, switch, or continue the initial biologic  2. To assess the clinical outcomes (e.g., reduction of exacerbations, long-term OCS use, asthma control) by biologic utilization patterns  3. To assess healthcare resource utilization (hospitalization, emergency room visits, invasive ventilation) by biologic usage patterns (not initiating, stopping, switching or continuing)	
Countries of study	Argentina, Australia, Bulgaria, Canada, Denmark, Colombia, Greece, Ireland, Italy, Japan, Kuwait, Mexico, Poland, Portugal, South Korea, Spain, Singapore, Saudi Arabia, Taiwan, UK, United States, UAE	
Author	[name]	

One of the promising ways of addressing all the severe asthma phenotypes may be via targeting one of the upstream inflammatory responses of the disease, such as the cytokine thymic stromal lymphopoietin (TSLP)[13]. TSLP is expressed by the airway epithelium in response to both allergic and non-allergic eosinophilic inflammation [14]. Lack of effective therapies for all patients with severe asthma, together with additional hurdles, such as accessibility or eligibility for more

Study Protocol: [OPCG-2005] Biologic Usage Patterns, Clinical Outcomes and Healthcare Resource Utilization (CLEAR)

than one biologic, have led to patients receiving sub-optimal or inappropriate biologics at initiation [11,12]. This can lead to various patterns of use, such as stopping or switching from the first biologic to a second, and in some cases, to a third or fourth biologic as clinicians and patients search deliberately for adequate response.

In an ISAR study on Biologic Utilization (prepublication) most patients (79%; 2791/3531) continued their first biologic, 10% (356/3531) stopped and 11% (384/3531) switched among patients who were followed up for at least a period of 6 months. This pattern was reproduced at the country level, although the ratio of 'stoppers' to 'switchers' varied. The most common reported reasons for stopping or switching a biologic was lack of efficacy benefits and/or adverse events. Disruption to the clinical management of biologics, most likely due to ineffective response and/or inappropriate initiation of the , may lead to a worsening of asthma control and an associated increase in health care utilization. This has yet to be demonstrated in a real-world setting or quantified. In addition, there may be a subgroup that is eligible yet is not reaping the benefits of targeted therapy.

#### 1.1 STUDY AIMS

This study will describe the patterns of biologic use or lack thereof and their clinical outcomes and healthcare resource uses in a real-life international cohort of patients with severe asthma.

#### 1.2 STUDY OBJECTIVES

The objectives of this study are as follows:

1. To describe the demographic and clinical characteristics (including biomarker characteristics), of five severe asthma patient groups based on patterns of biologic initiation (1. Initiated and switched, 2. Initiated and continued, 3. Initiated and stopped, 4. Not initiated but eligible for biologics, 5. Not initiated and not eligible for any biologics)

[figure not shown]

Figure 2 Chart depicting different severe asthma patient groups in CLEAR

\*All patients who have initiated biologics are considered to have met frequent eligibility criteria (eligibility criteria mentioned below)

- 2. To assess the clinical outcomes (e.g., reduction of exacerbations, long-term OCS, asthma control) across the biologic utilization patterns mentioned above
- 3. To assess the healthcare resource utilization (hospitalization, emergency room visits, non-invasive and invasive ventilation) depending upon which biologic is prescribed

#### 2. STUDY DESIGN

#### 2.1 INCLUSION AND EXCLUSION CRITERIA

#### Inclusion criteria:

- Patients' data entries from ISAR who are from countries that have at least two biologics available (defined as the presence of a license for the treatment of severe asthma),
- Patients, 18 years of age or older, with a diagnosis of severe asthma which requires treatment with guideline-suggested medications with 2018 GINA:

Study Protocol: [OPCG-2005] Biologic Usage Patterns, Clinical Outcomes and Healthcare Resource Utilization (CLEAR)

- Treatment Step 4 and being uncontrolled OR
- Treatment Step 5.
- Registry data for a minimum of one year prior to index date (defined as the date of biologic initiation for biologic patients and date of ISAR enrolment for non-biologic patients) and 24 weeks after therapy or enrolment,
- Data received by ISAR before July 2021

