#### Did not initiate:

- Not eligible: Did not meet the criteria for eligibility of biologic therapy and did not initiate any therapy
- Eligible: Eligible for biologic therapy but did not initiate any biologic therapy
- A "frequent-eligibility" criterion of each biologic class will be used to assess eligibility. This
  criterion will be constructed using the results from the ISAR biologic availability survey and
  will be subject to confirmation from the ISAR scientific steering committee (see Table 1 for
  possible criteria per biologic class)

[figure not shown]

Table 1: Frequent-Eligibility Criteria per Biologic Class. Patients who did not initiate biologic therapy and are eligible will meet any of the three criteria for any of the three biologic groups.

	Anti-lgE	Anti-IL5/5R	Anti-IL4/13
Background therapy	Met via ISAR inclusion criteria		
Positive Allergen test	Yes, AND	N/A	N/A
IgE levels	≥ 30 IU/mL, AND	N/A	N/A
BEC	N/A	≥ 150 cells/µL with long- term OCS, OR ≥ 300 cells/µL without long-term OCS, AND	≥150 cells/µL with long-term OCS, OR ≥300 cells/µL without long-term OCS, OR
FeNO	N/A	N/A	≥25 ppb, AND
Exacerbation OR Iong-term OCS	Pre-therapy exacerbation (≥2) OR On long-term OCS	Pre-therapy exacerbation (≥2) OR On long-term OCS	Pre-therapy exacerbation (≥2) OR On long-term OCS

The ISAR enrolment date will mark the start of the outcome period for those who did not initiate biologics while for those who did the index date will be signified by the First Biologic Therapy Start Date. A minimum of 16-weeks of follow-up time post biologic initiation (outcome period) will be applied in alignment with the ERS recommendation for time of biologic response assessment [8]. This is also congruent with the methodology used in the ISAR research project 'Defining and Characterizing Responders to Biologic TrEAtment in Severe AsthMa Patients (BEAM).' To assess the impact of this design, the study will evaluate and report the number of patients that had three types of follow-up data: 1.) <24 weeks, 2.) > 24 weeks to 1-year 3.) >1-year.

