**Primary outcome: Exacerbation** 

An asthma exacerbation will be defined as the occurrence of the following events (ERS/ATS task

force definition):

asthma-related hospital attendance/admission primary care consultation; AND/OR

asthma-related A&E attendance; AND/OR

an acute oral corticosteroid course of 3 days or more

separate recordings of exacerbations within a 14 day period will be treated as the

same exacerbation.

A time-to-event analysis will be performed to analyse the association between utilization pattern and time to first exacerbation with right censoring at the time of death, switching, stopping or loss to follow-up. Kaplan-Meier curves will be used to describe event-free survival over time and comparisons. Conditional Cox regression will be performed with time to the first exacerbation as the outcome variable (y) to estimate Hazard Ratios (HR) with 95% confidence intervals (CI) of the main effect. The proportional hazard assumption will be evaluated visually by means of a log-log

plot of survival.

As the dispersion of the exacerbation data is expected to be high and as this outcome is conditional on the duration of follow-up, we may apply a negative binomial regression (NBR) to estimate the reduced rate of exacerbation (y=annual rate of exacerbation). We switch to a count model to take advantage of all exacerbations at follow up. Group comparisons (e.g. gender, BMI, number of biologics available etc.) will be made if interaction between a group and biologic use pattern is found. We will also run a NBR using the total post-therapy/post-ISAR enrolment

exacerbations.

Secondary outcome: Asthma control

By applying a multinomial regression model (ordered), we will assess the probability or odds of the combined categories partially or controlled versus uncontrolled asthma for those that continue

compared to those that do not initiate or switch or stop.

Secondary outcome: long term oral corticosteroid (OCS) dose

20

Study Protocol: [OPCG-2005] Biologic Usage Patterns, Clinical Outcomes and Healthcare Resource Utilization (CLEAR)

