Steroid-sparing agent (specific drug can be found in current medication)
Enter into clinical trial
Other (please specify)

\*CAP immunoCAP test, CT computed tomography, DEXA dual energy X-ray absorptiometry, ELISA enzyme-linked immunosorbent assay, FeNO fractional exhaled nitric oxide,  $FEV_1$  forced expiratory volume in 1 second, FVC forced vital capacity, GINA Global Initiative for Asthma, ICS inhaled corticosteroids, IgE immunoglobulin E, IL-5 interleukin-5, ISAR International Severe Asthma Registry, LABA long-acting  $\beta_2$ -agonist, LAMA long-acting muscarinic antagonist, LTRA leukotriene receptor antagonist, PC20 provocative concentration of methacholine/histamine needed to produce a 20% decrease in  $FEV_1$ , PEF peak expiratory flow, RAST radioallergosorbent test, SPT skin prick test.

Asthma Control Questionnaire or the Asthma Control Test are optional extras for this category (depending on registry preference).

Other new biologics will be added once approved and in use.

Poor adherence to treatment can be indicated by selecting either (a) or (b):

[figure not shown]
- (a) Clinical impression: opinion of a medical personnel
  - E.g. i) Impression of 'non-persistence': patient stops taking medication.
  - ii) Impression of 'non-conformation': patient does not take medication as prescribed.
- (b) Prescription records: evidenced by medical records detailing prescriptions being issued and inadequately filled.
  - E.g. Medication possession ratio (MPR) = (Sum of days' supply for all fills/Number of days) x 100% <80% threshold.

Calls for a trained clinician's perception or opinion on any other external factors (if any) potentially contributing to the severe asthma symptoms.

E.g. Weather (cold air), air pollution, physical activity (exercise-induced asthma symptoms), occupational triggers (workplace irritants, gases, chemical fumes, dust), strong smells (perfumes), prior respiratory infections.

Aims to record the asthma action plan for a patient to review efficacy over time.

- E.g. i) Entry into clinical trial: If patient can benefit from a clinical trial drug.
- ii) Discharge to local asthma service: If patient has shown alleviated asthma symptoms.
  - iii) Optimisation of current asthma therapy: If patient's current asthma therapy is titrated for better asthma management.
- iv) Bronchial thermoplasty: If patient is eligible to have a surgery to manage their asthma.

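### Requiring 24 weeks of recorded post-index data excludes patients for events after index, conflicts with the 16-week minimum, and discards time that the exacerbation models could use

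*Protocol*

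**What the plan says.** Section 2.1 (Inclusion criteria) asks for registry data covering at least one year before index "and 24 weeks after therapy or enrolment". Index is "defined as the date of biologic initiation for biologic patients and date of ISAR enrolment for non-biologic patients". A separate bullet limits the study to data that ISAR received before July 2021. Neither bullet exempts patients who die or leave.

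Section 2.2, in the paragraph after Table 1, gives another figure: "A minimum of 16-weeks of follow-up time post biologic initiation (outcome period) will be applied". To gauge the effect of the design, it adds that "the study will evaluate and report the number of patients that had three types of follow-up data: 1.) <24 weeks", with two longer classes after that.

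Section 4.2 compares initiators with non-initiators first (Group comparisons). The primary exacerbation analysis is time to first event with "right censoring at the time of death, switching, stopping or loss to follow-up". A negative binomial model may follow, because the outcome depends on length of follow-up.

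In the Appendices, footnote 5 to Table S1 explains one management-plan category as "Discharge to local asthma service: If patient has shown alleviated asthma symptoms".

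**The concern.** The rule does not ask whether 24 weeks could have been observed before the data cut. It asks whether 24 weeks were recorded. A patient indexed too late for 24 weeks to elapse drops out for an administrative reason unrelated to prognosis. A patient who dies, leaves or is lost in week 10 drops out because of something that happened after index. The same protocol plans to censor at death and loss, so the entry rule removes patients whom the analysis was built to handle.

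The comparison at stake is initiators versus non-initiators, which needs no follow-up to assign the group. There are two reasons to think that early exit might not be alike in the two groups, and both are inferences:

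- Discharge can follow improvement, if discharge also ends registry follow-up.
- Section 2.3 says that ISAR holds retrospective data. An initiator whose biologic began well before enrolment has already stayed in view up to enrolment, whereas a non-initiator's 24 weeks start at enrolment.

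Even with no bias, valid events are lost and early deaths and exits by group go unreported.

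**Working it through.** **No plan figure to reproduce.** The readable text gives no exit rate, no death count and no split of the 3,532 feasible patients by length of follow-up. Every exit rate below is an assumption.

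**The rules side by side.** 24 weeks = 168 days and 16 weeks = 112 days, a gap of 56 days.

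- An initiator lost at week 20 is out under section 2.1 and meets the section 2.2 minimum.
- In a study population formed under section 2.1, the class below 24 weeks in section 2.2 is empty.
- A patient who exacerbates in week 6 and dies in week 10 would count as an event in the section 4.2 Cox model, but fails both minimums, so patient and event are absent.
- Under section 2.1, no death or loss can occur as a censoring time before day 168.

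**Simulation of the hazard ratio (HR).** Assumptions: 30,000 patients per group, gamma frailty with variance 1, mean exacerbation hazard about 1 per year, one year of follow-up, true HR 1.00. The HR is for the group with more exit against the group with less.

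| Annual exit | Who leaves more | Excluded by rule | Events lost | HR, censored at exit | HR, 24-week rule | Added by rule |
|---|---|---|---|---|---|---|
| 5% v 5% | unrelated to risk | 2.3% v 2.4% | 0.8% | 0.994 | 0.993 | 0.001 |
| 10% v 30% | unrelated to risk | 4.8% v 14.9% | 4.0% | 1.015 | 1.013 | none |
| 5% v 20% | higher risk | 2.2% v 9.1% | 3.4% | 0.943 | 0.923 | 0.020 |
| 10% v 30% | higher risk | 4.7% v 14.3% | 6.1% | 0.951 | 0.917 | 0.034 |
| 5% v 20% | lower risk | 2.4% v 9.5% | 1.6% | 1.010 | 1.020 | 0.010 |
| 10% v 30% | lower risk | 4.8% v 14.8% | 2.8% | 1.047 | 1.058 | 0.011 |

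Where exit was unrelated to risk, the two analyses of the same data differed by at most 0.004 (0.991 v 0.995, at 5% v 20%). The added 0.010 to 0.034 is above that noise. Where exit was related to risk and unequal, 0.010 to 0.057 of bias remained after censoring.

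**Closed-form check on the rate.** Assume exponential frailty with mean 1.5 exacerbations per year, no early exit among initiators and no treatment effect. Mean rate in the lower-risk half: 1.5 × (1 − ln 2) = 0.460. In the upper half: 1.5 × (1 + ln 2) = 2.540. If non-initiators leave early with probabilities a (lower half) and b (upper half), the retained rate is [(1 − a) × 0.460 + (1 − b) × 2.540] / [(1 − a) + (1 − b)].

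- a = 0.10, b = 0.02 (6% leave): 2.903 / 1.88 = 1.544; rate ratio 1.5 / 1.544 = 0.97.
- a = 0.20, b = 0.02 (11% leave): 2.857 / 1.78 = 1.605; rate ratio 0.93.
- a = 0.30, b = 0.05 (17.5% leave): 2.735 / 1.65 = 1.658; rate ratio 0.90 to 0.91.

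Now keep the leavers with 12 weeks each (0.23 year) and give retained patients one year. In the middle case, events = 1.4286 + 0.23 × 0.0714 = 1.4450 and person-years = 0.89 + 0.23 × 0.11 = 0.9153. The rate is 1.579 and the ratio 0.95. Across the three cases, crude person-time gives 0.98, 0.95 and 0.93; a negative binomial model with dispersion 1 and a person-time offset gives 0.98, 0.96 and 0.95. Keeping the leavers removes about a quarter to a half of the bias.

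**The case against.** Several points on the other side stand.

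- **Not selection on the study outcome.** A reader might infer that patients are removed by their own outcome. Table 3 lists exacerbations, control, oral steroid dose, admissions and emergency visits; death, discharge and loss are not among them. Nor is this immortal time for the primary event: an exacerbation in week 6 counts if the patient is still recorded at week 24.
- **Not hidden everywhere.** A reader might infer that early leavers vanish from every table. Section 2.2 plans counts by length of follow-up. If these are taken before section 2.1 is applied, short records would show there. But they are counts only: no reason for exit, no stated split by group, and nobody is returned to the analysis.
- **The discharge evidence is thin.** Footnote 5 illustrates a management-plan category. It does not say that discharge occurs within 24 weeks or ends registry follow-up.
- **Early leavers' time is only partly usable.** Section 3.2 measures outcomes at follow-up visits and counts exacerbations up to the current visit. Someone lost before any visit may contribute nothing, and asthma control and follow-up steroid dose need a post-index assessment.
- **The closed-form ratios are an extreme case.** They assume no early exit among initiators and ignore the matching and adjustment planned in section 4.2. They are not bias that the fix would cure.

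A statistical analysis plan could not readily repair this: an inclusion criterion belongs to the protocol, and a patient who was not admitted cannot be censored later.

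**Conclusion.** The point holds as a design weakness of modest size and as a contradiction between sections 2.1 and 2.2. Entry depends on data recorded after index, while the primary analysis could censor the same patients. A 16-week rule based on recorded data would have the same defect over a shorter window.

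Bias in the initiator versus non-initiator comparison requires early exit that is related to exacerbation risk and unequal between groups. The documents show neither, so a reader should not conclude that the comparison is biased by a known amount or in a known direction. Under the assumed rates, the rule added about 0.01 to 0.03 to the bias in the hazard ratio, towards or away from biologics depending on who leaves. That added part is what censoring removes; the bias from informative exit itself stays. With exit unrelated to risk there was no added bias, but up to 4.0% of events were discarded. The change is worth making because the records are already held, not because the estimate is known to be wrong.

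**What to change.** 1. Reconcile sections 2.1 and 2.2 on one minimum, and say whether it applies to non-initiators as well.
2. For the initiator versus non-initiator analyses of exacerbations and health resource use, replace the recorded-data rule with potential follow-up: index date at least the chosen minimum before the data cut.
3. Keep early leavers who have any ascertained post-index time, censored at last contact in the Cox model and with a person-time offset in the count model.
4. Count initiators who leave before a usage label can be assigned as initiators, unclassified. Someone lost at week 10 while still on treatment fits none of continued (at least 6 months), switched or stopped.
5. Apply a recorded minimum only to the continue, stop and switch comparisons and to outcomes that need a follow-up assessment.
6. Report deaths and other exits before 24 weeks by group, with reasons where recorded.

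Cost: a rewritten criterion in section 2.1, a small edit to the initiator definition in section 2.2 and under Group comparisons in section 4.2, and a re-extraction of records already held. Some short records with little information will enter. The change does not remove informative exit, the 6-month condition in the definition of continued, or any difference arising because some initiators' index dates precede enrolment.

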#### **Exclusion criteria:**

- Having received bronchial thermoplasty
- Less than 18 years of age at biologic initiation or ISAR enrolment

#### 2.2 STUDY DESIGN AND SAMPLE SIZE

The study sample will be drawn from the ISAR population during the time of data collection. This study will first ascertain the following patterns of biologic use:

#### Initiated

- Continued: use of first biologic for at least 6 months, without indication of stopping or switching
- **Switched**: stopped the initial biologic and received a (one or more) different biologic, without restriction of any time lapse between biologics
- **Stopped**: stopped the initial biologic and did not receive another biologic. Caution will be taken as stoppers maybe on the path to switchers. Therefore, data will be reviewed to add a feasible follow-up time post stopping and free of not starting another biologic to ascertain true stoppers.

Study Protocol: [OPCG-2005] Biologic Usage Patterns, Clinical Outcomes and Healthcare Resource Utilization (CLEAR)

#### Did not initiate:

- Not eligible: Did not meet the criteria for eligibility of biologic therapy and did not initiate any therapy
- Eligible: Eligible for biologic therapy but did not initiate any biologic therapy
- A "frequent-eligibility" criterion of each biologic class will be used to assess eligibility. This
  criterion will be constructed using the results from the ISAR biologic availability survey and
  will be subject to confirmation from the ISAR scientific steering committee (see Table 1 for
  possible criteria per biologic class)

[figure not shown]

Table 1: Frequent-Eligibility Criteria per Biologic Class. Patients who did not initiate biologic therapy and are eligible will meet any of the three criteria for any of the three biologic groups.

	Anti-lgE	Anti-IL5/5R	Anti-IL4/13
Background therapy	Met via ISAR inclusion criteria		
Positive Allergen test	Yes, AND	N/A	N/A
IgE levels	≥ 30 IU/mL, AND	N/A	N/A
BEC	N/A	≥ 150 cells/µL with long- term OCS, OR ≥ 300 cells/µL without long-term OCS, AND	≥150 cells/µL with long-term OCS, OR ≥300 cells/µL without long-term OCS, OR
FeNO	N/A	N/A	≥25 ppb, AND
Exacerbation OR Iong-term OCS	Pre-therapy exacerbation (≥2) OR On long-term OCS	Pre-therapy exacerbation (≥2) OR On long-term OCS	Pre-therapy exacerbation (≥2) OR On long-term OCS

The ISAR enrolment date will mark the start of the outcome period for those who did not initiate biologics while for those who did the index date will be signified by the First Biologic Therapy Start Date. A minimum of 16-weeks of follow-up time post biologic initiation (outcome period) will be applied in alignment with the ERS recommendation for time of biologic response assessment [8]. This is also congruent with the methodology used in the ISAR research project 'Defining and Characterizing Responders to Biologic TrEAtment in Severe AsthMa Patients (BEAM).' To assess the impact of this design, the study will evaluate and report the number of patients that had three types of follow-up data: 1.) <24 weeks, 2.) > 24 weeks to 1-year 3.) >1-year.

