First the demographic and clinical characteristics as mentioned in section 3.1 will be described in detail per group. This will include describing proportions on patients from each group based on their biomarkers, long term OCS (LTOCS) use, baseline demographics such as those outlined in Section 3.1. Next, the significant difference in level of T2 phenotypes and demographic or clinical characteristics (section 3.1) across the five groups will be compared and tested for statistical significance via Chi-square tests for comparison of counts data, and t-test or one-way analysis of variance (ANOVA) for continuous variables. Where appropriate, McNemar tests, paired t-tests will be considered. Statistical significance will be defined as p <0.05. Stata version 14.2 (College Station, TX, USA) will be used to conduct all statistical analyses and data manipulations.

Additionally, comparisons will be made as follows:

Study Protocol: [OPCG-2005] Biologic Usage Patterns, Clinical Outcomes and Healthcare Resource Utilization (CLEAR)

- 1. Switch vs. continue
- 2. Stop vs. continue
- 3. Patient received biologics vs. eligible but did not receive biologics
- 4. Biologic eligible (biologic users+ non-users but who qualify) vs. not eligible.

#### 4.2 OBJECTIVE 2

As there are various factors underpinning the probability of not receiving, receiving, continuing, switching, or stopping a biologic, comparing the clinical outcomes set forth in section 3.2 will need careful consideration. One of the main confounders to consider is the availability and/or accessibility of multiple biologics in a country. Therefore, all countries included in the analysis of assessing the clinical outcomes across biological utilization groups will have at least 2 biologics available in the market (availability defined as licensed in the country) at the time of the patient's enrolment into ISAR (index date). There will be a cut-off date of 01 Jan 2014 for assessment of clinical outcomes to ensure the availability of drugs in the market.

Furthermore, according to the results of objective 1 (pre-therapy or baseline characteristics), before assessing for differences in the clinical outcomes across groups, baseline imbalance will be examined across groups and matched accordingly. Prior to this step, the clinical outcomes of each group will be described.

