Standardized mean difference (SMD) will be used to quantify differences in both continuous and categorical variables between the biologic utilization groups at baseline. An SMD  $\leq$  10% indicates sufficient balance between treatment groups. It is hypothesized that data completeness will vary between treatment groups. Therefore, propensity score matching methodology is envisioned at the stage of comparing between groups to conserve the statistical power. After the matching approach, the SMD will be recalculated to verify the accuracy of the model. If residual confounders are present, they will be entered into the respective multivariate model noted below. Clinical and/or health resource outcomes may be affected by the level of eosinophilic phenotypes, thus, results may be stratified by level of ISAR Eosinophilic Grade.

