# 11.APPENDICES

Table S1. Full list of ISAR 95 core variables

Category	Variable field name	Recorded units
	Highest blood eosinophil count within the past year	Decimal number
Blood/Sputum	Date of the highest blood eosinophil count within the past year	DD/MM/YYYY
	Was this the highest blood eosinophil count during an exacerbation event?	No/Yes
	The highest blood eosinophil count within the past year and not during exacerbation	Decimal number
	Date of highest blood eosinophil count within the past year and not during an exacerbation event	DD/MM/YYYY
	Current blood eosinophil count	Decimal number
	Date of current blood eosinophil count	DD/MM/YYYY
	The highest sputum eosinophil count within the past year (percentage)	Decimal number
	Date of the highest sputum eosinophil count within the past year	DD/MM/YYYY
	IgE count	Decimal number
	Chest CT scan	Normal/Abnormal/Not done
Diamagatica	Date of chest CT scan	DD/MM/YYYY
Diagnostics	Bone densitometry (DEXA)	No/Yes
	Date of bone densitometry (DEXA)	DD/MM/YYYY
	Pre-bronchodilator FEV₁	Decimal number
	Post-bronchodilator FEV₁	Decimal number
Lung function	Pre-bronchodilator FVC	Decimal number
Lang laneaon	Post-bronchodilator FVC	Decimal number
	Predicted FEV₁	Decimal number (auto- calculated)

	Pre-bronchodilator FEV₁ (% predicted)	Decimal number (auto- calculated)
	Post-bronchodilator FEV₁ (% predicted)	Decimal number (auto- calculated)
	Predicted FVC	Decimal number (auto- calculated)
	Pre-bronchodilator FVC (% predicted)	Decimal number (auto- calculated)
	Post-bronchodilator FVC (% predicted)	Decimal number (auto- calculated)
	FEV₁/FVC ratio pre-bronchodilator (%)	Decimal number (auto- calculated)
	FEV₁/FVC ratio post-bronchodilator (%)	Decimal number (auto- calculated)
	PC20 methacholine/histamine test	No/Yes
	Date of PC20 test	DD/MM/YYYY
	PC20 test result	Decimal number
	FeNO test	No/Yes
	Date of FeNO test	DD/MM/YYYY
	FeNO test result	Decimal number
Allergen testing	Environmental allergen test	Serum allergen test (CAP, ELISA, RAST)/SPT/not done
	Serum allergy test: Positive to perennial allergen	No/Yes
	Serum allergy test: Specify positive allergen and result	Dust mite (e.g. D. pteronyssinus)/grass mix/cat hair/mould mix/dog hair/Aspergillus/other (please specify)
	Date of serum allergy test	DD/MM/YYYY
	SPT: Positive to allergen	No/Yes
	SPT: Specify positive allergen and result	Grass mix/trees/weed mix/Aspergillus/mould mix/dust mite/food mix/animal mix/cat

		hair/dog hair/other (please specify)

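### Section 2.2 defines the not-eligible group by default, so a non-initiator who lacks a deciding biomarker test falls, read literally, into group 5

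*Protocol*

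**What the plan says.** Section 2.2 splits non-initiators in two. The eligible side is defined under Table 1: "Patients who did not initiate biologic therapy and are eligible will meet any of the three criteria for any of the three biologic groups". The other side is whatever remains: "Not eligible: Did not meet the criteria for eligibility of biologic therapy and did not initiate any therapy". Section 1.2 lists five groups, none of them for undetermined eligibility. Section 2.1 asks for registry time before and after the index date. It neither requires biomarker results nor excludes patients without them.

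Table 1 uses an allergen test with IgE for anti-IgE, the blood eosinophil count (BEC) for anti-IL5/5R, and BEC or FeNO for anti-IL4/13. All three columns end in the same condition: "Pre-therapy exacerbation (≥2) OR On long-term OCS". The criteria are still provisional; they "will be subject to confirmation from the ISAR scientific steering committee".

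Initiators do not go through this check. The note to Figure 2 in Section 1.2 says: "All patients who have initiated biologics are considered to have met frequent eligibility criteria".

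The registry form foresees missing tests. In Table S1 the allergen field takes the values "Serum allergen test (CAP, ELISA, RAST)/SPT/not done", and a separate field records whether FeNO was tested at all. Section 4.2 adds: "It is hypothesized that data completeness will vary between treatment groups".

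**The concern.** Not having met a criterion and having been shown not to meet it are different things when a test may never have been done. The definition does not separate them, and the five-group scheme offers an untested, non-qualifying patient no place other than group 5. Because initiators are deemed eligible without any test, only the non-initiator groups depend on what was recorded.

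Group membership is the exposure in this study, and the Protocol itself fixes it. Two of the four contrasts listed in Section 4.1 use the split: recipients against eligible non-recipients (contrast 3), and "Biologic eligible (biologic users+ non-users but who qualify) vs. not eligible" (contrast 4). Section 1 also raises the possibility of an eligible subgroup that misses out on targeted therapy. Group 4 is the measure of that subgroup, and it would be too small.

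**Working it through.** **1. Which untested patients can be misplaced.** The Protocol gives no figure to reproduce, so the check starts from the logic of Table 1. Each of four items (allergen test, IgE, BEC against the threshold for the patient's OCS status, FeNO) is taken as met, not met or untested. The exacerbation/OCS condition is taken as known. The anti-IL4/13 column is read as (BEC or FeNO) and the condition. When the condition is met, eligibility reduces to:

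(allergen and IgE) or BEC or FeNO

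There are 3^4 = 81 patterns, of which 2^4 = 16 are fully tested. That leaves 81 − 16 = 65 with at least one untested item.

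| Exacerbation/OCS condition | Still eligible | Definitely not eligible | Undetermined | Total |
|---|---|---|---|---|
| Met | 36 | 2 | 27 | 65 |
| Not met | 0 | 65 | 0 | 65 |

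The 27 can be counted by hand. No class may be met, so BEC and FeNO are each not met or untested (2 × 2 = 4 combinations). The allergen/IgE pair must be either failed (5 of its 9 states) or open (3 of 9). This gives 8 × 4 = 32 patterns. In 5 of them all three parts have failed outright, and 32 − 5 = 27 remain. These are counts of patterns, not shares of patients.

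Examples:
- FeNO untested, BEC met, condition met: eligible, no error.
- All four untested, condition not met: correctly not eligible.
- FeNO untested, the other three not met, condition met: undetermined, and sent to group 5 by the literal rule.

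**2. Direction.** Group 4 requires a class to be met on recorded results, so an untested item cannot add a false member. It can only remove a true one, who then goes to group 5.

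**3. Size, by illustration only.** Let p be the share of non-initiators who are truly eligible, and m the share of those whose eligibility cannot be shown on recorded results. Neither is in the Protocol. m is not the missing rate of any single test, since a patient may qualify by another route.

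- Labelled not eligible: (1 − p) + p·m
- Share of that group truly eligible: c = p·m / [(1 − p) + p·m]
- Labelled eligible: p·(1 − m)

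For p = 0.6 and m = 0.3: c = 0.18 / (0.40 + 0.18) = 0.18 / 0.58 = 31%. Group 4 holds 0.6 × 0.7 = 42% of non-initiators instead of 60%.

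| p | m = 0.1 | m = 0.3 | m = 0.5 |
|---|---|---|---|
| 0.4 | 6% | 17% | 25% |
| 0.6 | 13% | 31% | 43% |
| 0.8 | 29% | 55% | 67% |

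If the eligible patients who cannot be shown to be so resemble the other eligible non-initiators, a true difference between groups 4 and 5 in a recorded characteristic shrinks to (1 − c) of its value: 1 − 0.31 = 69% in the worked case.

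**4. Which analyses use the split.** Contrasts 3 and 4 in Section 4.1 do. Under Group comparisons in Section 4.2, outcomes are compared between initiators and non-initiators, and between those who stopped or switched and those who continued. The asthma-control model likewise takes non-initiators together. Moving a patient between groups 4 and 5 changes none of these.

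**The case against.** The strongest reply is that the Protocol nowhere says that untested means ineligible. It is silent, Table 1 is provisional, the group chart and feasibility diagram are not visible, and handling of missing values is often left to an SAP. This stands as far as it goes: the misplacement follows from the wording and is not stated as a rule. But the definition and the five groups leave no other destination, and confirming the thresholds would not change that.

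A reader might infer that every non-initiator with an untested marker is counted as ineligible. Table 1 does not support this. Patients who fail the exacerbation/OCS condition are rightly in group 5, and many others qualify by another route.

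A reader might also infer that the outcome comparisons are biased. Those named in Section 4.2 pool non-initiators. Only an outcome summary that separates groups 4 and 5, as the general wording of Objective 2 allows, would be affected.

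Three further points stand in part. The remark on data completeness in Section 4.2 concerns treatment groups and is there to justify matching, so it is only indirect support. Table S1 shows that allergen and FeNO tests can be absent; for BEC, which serves two classes, it neither shows this nor establishes completeness. Section 4.1 plans to report the percentage non-missing per variable, which would reveal untested markers in group 5 but would not correct the labels.

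**Conclusion.** The point holds in a limited form and should be fixed. Taken literally, Section 2.2 places in group 5 those non-initiators who meet the exacerbation/OCS condition, qualify under no class on recorded results, and lack a test that could have qualified them. Group 5 is contaminated; group 4 is undercounted but gains no false members. Contrast 4 sets the eligible side against a mixed group. Contrast 3 is biased only if the eligible non-initiators who can be identified differ from those who cannot, which the Protocol neither shows nor excludes.

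The size is unknown. The 6% to 67% range in the table reflects assumed values of p and m and is not an estimate. The conclusion rests on the literal reading of the definition, on the reading of the anti-IL4/13 column given above, and on there being no missing-data step in the figures or in an SAP that was not available.

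**What to change.** In Section 2.2, with whatever thresholds the steering committee confirms:

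- Define *not eligible* as a non-initiator who fails the exacerbation/OCS condition, or whose recorded results are enough to rule out all three classes.
- Label the remaining non-initiators who do not qualify *eligibility not determinable*, and report their number.
- Leave them out of groups 4 and 5 in the main Objective 1 contrasts. They stay among the non-initiators in the pooled outcome comparisons.
- Repeat the affected contrasts with all of them assigned to group 4, then all to group 5. The second run reproduces the literal rule.

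The cost is a sentence or two of text and two extra runs on data already held. Groups 4 and 5 become smaller, and the main contrasts are restricted to patients whose eligibility can be determined, which is itself a selection. The two sensitivity runs bound the group sizes and show the contrasts at both extremes of assignment.
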